4.2.1.2 Unsolicited AEs

Unsolicited AEs includes both serious (SAEs) and non-serious unsolicited AEs.

4.2.1.2.1 Presence

An observation will be considered an event if it has at least a verbatim term and is not Grade 0 intensity event.

Grade 0 events are not included in safety analysis but are included in separate listings.

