4.2.1.2.2 Intensity

Intensity will be derived according to the following classification:

• None, Grade 1, Grade 2, Grade 3, or Missing.

If the unsolicited AE is measurable and its preferred term is part of the list of solicited reactions, then the measurement is derived based upon and following the same rule of the intensity scales defined in the Section 5.3.1.2 for that measurable injection site or systemic reaction. Note the intensity could be considered as "None" (not a reaction) in the analysis despite being considered a reaction by the investigator (e.g., swelling measurement >0 mm but < 25 mm in adults). Intensity for the other unsolicited AEs will correspond to the value reported in the CRF. The maximum intensity corresponds to the highest intensity for a unique term.

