4.2.1.3 SAEs (including AESIs)

An event will be considered as a serious event if "Yes" is checked for "Serious" in the CRF.

An event will be considered as an AESI if "Yes" is checked for "Is the event an AESI?" in the CRF.

SAEs (including AESIs) will be analyzed throughout the study using the following periods:

- Within 7 days after vaccination
- Within 30 days after vaccination
- During the study (i.e., all SAEs occurred during the study), including the 6-month follow-up period

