4.2.1.4 Medically-Attended Adverse Event (MAAE)

An event will be considered as an MAAE if "Yes" is checked for "Is the event an MAAE?" in the CRF.

MAAE will be analyzed during the following time periods:

- Within 7 days after vaccination
- Within 30 days after vaccination
- During the study (i.e., all MAAEs occurred during the study), including the 6-month follow-up period.

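### The Grade 0 exclusion in SAP 4.2.1.2.1 has no exception for serious or medically-attended events, so an unsolicited pyrexia recorded below 38.0°C drops out of the SAE and MAAE tables

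*SAP*

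**What the plan says.** SAP 4.2.1.2 sets the scope: "Unsolicited AEs includes both serious (SAEs) and non-serious unsolicited AEs". SAP 4.2.1.2.1 then defines presence: "An observation will be considered an event if it has at least a verbatim term and is not Grade 0 intensity event". It adds: "Grade 0 events are not included in safety analysis but are included in separate listings". It states no exception for serious, special-interest or medically-attended events.

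SAP 4.2.1.2.2 governs intensity. "If the unsolicited AE is measurable and its preferred term is part of the list of solicited reactions, then the measurement is derived" on the scales for solicited reactions, and the result may be None "in the analysis despite being considered a reaction by the investigator". SAP 4.1.1.3.3 requires intensity for every unsolicited AE, serious or not, and grades fever by the solicited scale. In SAP Table 4.2 that scale starts at 38.0°C (100.4°F).

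Other sections point the other way. SAP 4.2.1.3 identifies an SAE by a CRF tick-box and describes the whole-study period as "all SAEs occurred during the study". SAP 4.2.1.4 does the same for MAAEs: "all MAAEs occurred during the study". Neither mentions intensity.

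SAP 4.2.1.5.5 gives three rules for AEs leading to discontinuation. The disposition table uses the completion form alone. The safety overview uses the completion form or an event of at least Grade 1 (for unsolicited events, also missing grade). The SOC/PT table uses only the graded event.

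**The concern.** Whether an event is serious, or was taken to a health care provider, does not depend on a measured intensity. SAP 4.1.1.1 keeps serious and severe apart. It defines an MAAE by the seeking of unplanned medical advice, counts telephone and email contact, and disregards the outcome of the contact. A temperature threshold on SAEs and MAAEs cuts across both definitions.

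Take an infant admitted for fever whose recorded temperature is 37.9°C, or one whose parent telephoned a clinic about the same reading. The investigator ticks *Serious* or *MAAE*, and the presence rule then says the observation is not an event. Describing safety is this trial's only objective, so the SAE and MAAE tables are among its main products. As the text stands, two programmers could follow different sections and produce different tables.

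**Working it through.** The plan gives no figure to reproduce here, so the check follows the rules through in order.

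**Inputs**
1. Scope: unsolicited AEs include SAEs (SAP 4.2.1.2). MAAEs up to D30 after each vaccination are recorded as unsolicited AEs (SAP 4.1.1.3.5).
2. Presence: not Grade 0 (SAP 4.2.1.2.1).
3. Grading: from the measurement if the preferred term is on the solicited list (SAP 4.2.1.2.2). That section refers to SAP 5.3.1.2 for the scales, but 5.3.1.2 is Causality. SAP 4.1.1.3.3 leads to the right place, Tables 4.1 and 4.2.
4. Assumption: Grade 0 is not defined. It is read here as the None of SAP 4.2.1.2.2, the only workable reading.

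**Fever (Table 4.2), using °F = °C × 9/5 + 32**

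| Recorded °C | °F | Derived intensity | Result under 4.2.1.2.1 |
|---|---|---|---|
| 37.5 | 99.5 | None | listing only |
| 37.9 | 100.22 | None | listing only |
| 38.0 | 100.4 | Grade 1 | tabulated |
| 38.5 | 101.3 | Grade 1 | tabulated |
| 38.6 | 101.48 | Grade 2 | tabulated |
| 39.6 | 103.28 | Grade 3 | tabulated |
| not recorded | – | Missing | tabulated (missing is not Grade 0) |

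**Erythema and swelling (Table 4.1).** Grade 1 runs from above 0 mm to below 25 mm. A size of 0 mm gives None, 1 mm and 24 mm give Grade 1, 25 mm gives Grade 2 and 50 mm gives Grade 3. Any positive size is therefore kept. The example in SAP 4.2.1.2.2 of a swelling below 25 mm that does not count is for adults.

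**AESIs (SAP 4.1.1.3.4).** Generalized seizures, Kawasaki disease, Guillain-Barré syndrome and ITP do not code to a solicited preferred term, so the filter does not reach them.

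**Does another section exempt SAEs or MAAEs?** SAP 4.2.1.3 and 4.2.1.4 both begin from an event, which is the term that 4.2.1.2.1 restricts. Their *all* explains an analysis period and grants no exemption. Elsewhere the SAP says so when a rule covers only non-serious events: 5.3.1.1 on the missing *Immediate* field, 5.3.1.4 on missing intensity, and the unsolicited row of Table 5.2. SAP 4.2.1.2.1 has no such limit.

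**Result.** What is affected is an unsolicited SAE or MAAE with preferred term Pyrexia and a recorded temperature below 38.0°C. The treatment is also uneven: a fever MAAE with no recorded temperature is counted, and one recorded at 37.9°C is not.

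**The case against.** The strongest reply is that the sections specific to SAEs and MAAEs should prevail over a general presence rule. They classify by tick-box and speak of all such events. Intensity is also absent from the SAE endpoint (SAP 4.1.1.2), from the SAE summary in SAP 5.1.1.2.1 and from the SAE row of Table 5.2. This is fair evidence of intent for SAEs. It is weaker for MAAEs, whose endpoint and table row do include intensity. In neither case does it override the presence rule, which covers SAEs by its own scope statement. If the intent was to count every ticked event, the SAP contradicts itself and needs the correction all the same.

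The second reply is that 38.0°C is the protocol's own definition of fever, and that Protocol 9.1.1.3.3 says unsolicited fever is analysed on the solicited scale. That stands for non-serious events that were not medically attended. It does not justify removing an event that was ticked because of hospitalisation or medical contact.

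The limits on reach also stand. A prelisted reaction starting from D0 to D07 is solicited, so fever in that window falls outside this rule. Excluded events remain in listings, and expedited SAE reporting is untouched.

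**Conclusion.** Wrong as written. Taking Grade 0 as None, the SAP leaves an unsolicited pyrexia SAE or MAAE recorded below 38.0°C out of the SAE and MAAE tables, contrary to its own promise to analyse all of them. Few SAEs should be affected. MAAEs are more exposed because a telephone call is enough to qualify.

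Three stronger inferences are tempting, and the documents do not support them.

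- *That the discontinuation percentages lose these events generally.* Only the SOC/PT table in SAP 4.2.1.5.5 depends solely on grade. A subject with *Adverse Event* as completion status stays in the disposition and overview tables. What remains is a possible mismatch: a subject counted there with no matching SOC/PT entry.
- *That the pharmacovigilance reconciliation would fail.* Protocol 11.2 reconciles two databases before release for analysis. The Grade 0 rule acts later and changes neither.
- *That a number of lost infants can be given.* The documents give neither a fever MAAE rate nor the share of such events recorded below 38.0°C. Any such number would also overstate the change in the percentage with at least one MAAE, because an infant with another MAAE still counts.

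**What to change.** In SAP 4.2.1.2.1, limit the Grade 0 exclusion to non-serious unsolicited AEs that are not ticked as AESI, MAAE or *Caused Study Discontinuation*. State that every event ticked as serious or in one of those fields is tabulated whatever its derived intensity, shown as None where intensity is displayed. Say in the same place that Grade 0 means None. Add a matching sentence to SAP 4.2.1.3 and 4.2.1.4, and align the SOC/PT rule in SAP 4.2.1.5.5.

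This costs a short SAP edit and one programming condition. It needs no new data and no change in study conduct. The downside is that a few events will appear in the tables with intensity None.

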4.2.1.2.2 Intensity

Intensity will be derived according to the following classification:

• None, Grade 1, Grade 2, Grade 3, or Missing.

If the unsolicited AE is measurable and its preferred term is part of the list of solicited reactions, then the measurement is derived based upon and following the same rule of the intensity scales defined in the Section 5.3.1.2 for that measurable injection site or systemic reaction. Note the intensity could be considered as "None" (not a reaction) in the analysis despite being considered a reaction by the investigator (e.g., swelling measurement >0 mm but < 25 mm in adults). Intensity for the other unsolicited AEs will correspond to the value reported in the CRF. The maximum intensity corresponds to the highest intensity for a unique term.

4.2.1.2.3 Last Vaccination

Last vaccination before an unsolicited AE is derived from the start date of the unsolicited AE provided in the CRF and is calculated as follows:

- If an unsolicited AE has a complete start date and different to any of the vaccination dates, the start date is used to determine the last vaccination before the unsolicited AE.
- If the start date is missing or partially missing, or equal to any vaccination date, then the visit number in the "Appeared after Visit" or similar field, is used to determine the last vaccination before the unsolicited AE.

4.2.1.2.4 Time of Onset

Time of onset is derived from the start date of the unsolicited AE and the date of last vaccination as described in Section 4.2.1.2.3

Time of Onset = start date of the unsolicited AE – date of last vaccination before the unsolicited AE

The time of onset should be considered as missing only if one or both dates are missing or partially missing.

The unsolicited AEs will be analyzed "Within 30 days", which corresponds to AEs with a time of onset between 0 and 30 days after each vaccination or missing. An AE with missing time of onset will be considered to have occurred just after the vaccination (computed according to Section 4.2.1.2.3), so will be included in these tables. Time of onset period is displayed as D0-D3, D4-D7, D8-D14, D15 or later, and Missing.

Note: Unsolicited AEs that occurred before vaccination (negative time of onset) or with a time of onset higher than defined above will not be included in the safety analysis but will be listed.

4.2.1.2.5 **Duration**

Duration is derived from the start and end dates of the unsolicited AE: Duration = End date of unsolicited AE - start date of unsolicited AE + 1.

The duration should be considered as missing only if one or both of the start and end dates of the unsolicited AE is missing or partially missing.

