5.3.1.5 Start Date and End Date

Missing or partially missing start dates for unsolicited AEs will remain missing and not be imputed. If either the start or stop date is missing or partially missing, the time of onset will be considered to be missing. Nevertheless, unsolicited AEs with missing time of onset will be included in analyses according to the visit collected.

Missing or partially missing stop dates for AEs (solicited reactions and unsolicited AEs) will remain missing and not be imputed.

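### An unsolicited AE with a partly missing start date is counted within 30 days of the last dose even when its known month shows onset after D30

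*SAP*

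**What the plan says.** Three SAP sections act together.

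- **4.2.1.2.3 (Last Vaccination)** decides which dose an event belongs to: "If the start date is missing or partially missing, or equal to any vaccination date, then the visit number in the" Appeared after Visit field, or a similar one, is used. The field picks the dose. It is not used to place the event in time.
- **4.2.1.2.4 (Time of Onset)** defines onset as start date minus date of last vaccination: "The time of onset should be considered as missing only if one or both dates are missing or partially missing". Then: "An AE with missing time of onset will be considered to have occurred just after the vaccination", and such events go into the within-30-days tables. A closing note excludes onsets beyond the window, but it needs an onset that can be computed. Onset period is displayed with a separate Missing category.
- **5.3.1.5 (Start Date and End Date)** confirms that nothing is recovered from a partial date: "Missing or partially missing start dates for unsolicited AEs will remain missing and not be imputed". It adds that "unsolicited AEs with missing time of onset will be included in analyses according to the visit collected".

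On scope, 4.2.1.2 states: "Unsolicited AEs includes both serious (SAEs) and non-serious unsolicited AEs". Sections 4.2.1.3 (SAEs) and 4.2.1.4 ("MAAE will be analyzed during the following time periods") list 7-day, 30-day and whole-study periods and give no onset rule of their own. Table 5.2 has D0-D30 and D31-to-next-visit rows for both SAEs and MAAEs.

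**The concern.** A date with only the day missing still carries information. Take an MAAE dated only to the fourth calendar month after the month of dose 3. Three full calendar months lie between, at least 28 + 31 + 30 = 89 days, so it cannot have started before D90. The SAP still counts it within 30 days of dose 3.

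After dose 4 the visit may help as well. An event recorded as appearing after a Visit 5 held later than D30 is necessarily late, provided that the CRF field accepts Visit 5.

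Partial dates are most plausible where recall is longest: the diary card kept from Visit 3 to Visit 4, and the memory aid and telephone interview up to 6 months after dose 4. Most of the time in those intervals lies outside D0-D30. The trial is purely descriptive, so the per-dose percentages are its result. A rule that adds late background events mostly after doses 3 and 4 can create an apparent rise by dose, and it empties the D31-to-next-visit rows by the same number.

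**Working it through.** The plan states no figure on this point, so there is nothing to reproduce. The check is how far the rule could move the D0-D30 counts.

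**Inputs**

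- Window D0-D30: 31 days.
- Follow-up after doses 1 and 2: 60 (+14) days, so L = 60 to 74 (protocol 5.1.4).
- Follow-up after dose 3: age 164 to 224 days at Visit 3 (Table of Study Procedures). Visit 4 falls at 12 months and before 13 months, taken as 365 to 395 days. L = 365 − 224 = 141 to 395 − 164 = 231, nominally 180. The 24-week footnote (168 days) would give 395 − 168 = 227 as the upper limit.
- Follow-up after dose 4: 180 (+30) days, so L = 181 to 211 counting D0.
- Fraction m of events with a partial start date: not in the documents. Assumed 1% to 5%.

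**Model.** Constant event rate r per day, with m independent of onset time.

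- True D0-D30 count: 31r.
- Count under the SAP rule: (1 − m)·31r + m·L·r.
- Relative inflation: m(L − 31)/31.

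| Dose | L (days) | Beyond D30, (L − 31)/L | m = 1% | m = 5% |
|---|---|---|---|---|
| 1, 2 | 60 to 74 | 48% to 58% | 0.9% to 1.4% | 4.7% to 6.9% |
| 3 | 141 / 180 / 231 | 78% / 83% / 87% | 3.5% / 4.8% / 6.5% | 17.7% / 24.0% / 32.3% |
| 4 | 181 to 211 | 83% to 85% | 4.8% to 5.8% | 24.2% to 29.0% |

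Example, dose 4 at m = 5%: 0.05 × (181 − 31)/31 = 24.2%.

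**Where the misplaced events fall.** With equal rates after each dose and L = 60, 60, 180, 181, doses 3 and 4 supply (149 + 150)/(29 + 29 + 149 + 150) = 299/357 = 84% of them. Over the visit windows the range is 75% to 87%.

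**From events to subjects.** The figures above are event counts. A subject who already has an early event is not counted again. As an illustration, assume Poisson events and a 24.2% inflation.

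- Mean 0.5 early events per subject: the subject percentage goes from 1 − exp(−0.5) = 39.3% to 1 − exp(−0.621) = 46.3%, a relative rise of about 18%.
- Mean 1.0: from 63.2% to 71.1%, about 13%.

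**What the known date can recover.** Averaged over 1,461 consecutive dose dates, the first day of the onset month lies after D30 for 49% to 66% of late onsets after doses 1 and 2, 87% to 93% after dose 3, and 90% to 92% after dose 4. Using it cuts the dose 4 inflation at m = 5% from 24.2% to 24.2% × (1 − 0.902) = 2.4%.

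**What the visit can recover.** This applies to dose 4 only. Visit 5 is at D30 to D51 in the protocol (to D44 in the SAP table), so 87% to 100% of the post-D30 days come after it.

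**The case against.** Counting a missing onset as post-vaccination is an openly stated, conservative convention. It applies to both arms, no hypothesis is tested, and the Missing row of the onset display makes the events visible. All of that is true. It does not correct the 30-day totals, which still include these events, and late background events added to both arms pull a true early ratio between arms toward 1.

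Data cleaning will also limit m. Sites clarify diary entries, missing information must be explained, and queries are closed before lock. SAEs carry 24-hour reporting and source records, so they are probably well dated. This stands: m may be small, and the point concerns MAAEs more than SAEs.

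For ordinary non-serious AEs the default may be reasonable. The procedures table and the section on unsolicited AEs limit recording to 30 days, although the study design section says until the next visit.

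A reader might infer more than the documents support:

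- **That the visit field shows late onset after dose 3.** For doses 1 to 3 it covers the whole interval to the next vaccination, so only the known month can show it. For dose 4 the CRF is not available to confirm that the field accepts Visit 5, and a Visit 5 on D30 does not exclude onset that day.
- **That SAE and MAAE windows are certainly affected.** This is an inference from 4.2.1.2 and from the absence of another rule. SAP 4.1.1.3.5 records MAAEs as unsolicited AEs only up to D30, which leaves their later handling unclear.
- **That D0-D7 counts are inflated too.** SAP 4.2.1.2.4 names only the 30-day tables, and the MAAE row of Table 5.2 has no D0-D7 window.
- **That 5% to 24% is the error in the reported percentages.** It is a change in event counts under an assumed m.

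**Conclusion.** The point holds as a defect of the rule. Followed as written, SAP 4.2.1.2.4 counts within 30 days some events whose known month shows that they started later, and nothing elsewhere in the SAP removes them.

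The direction (D0-D30 rows too high, D31-to-next-visit rows too low) and the concentration after doses 3 and 4 follow from the text and the visit schedule. That holds on the literal reading that the rule governs the MAAE and SAE windows.

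The size is not known. The 5% to 24% after dose 4, against 1% to 5% after doses 1 and 2, rests on a constant event rate and an assumed 1% to 5% of partial dates independent of onset. Whole-study SAE and MAAE totals are unaffected. The documents do not support a claim of material bias between the arms. Label: cheap improvement.

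**What to change.** In SAP 4.2.1.2.4, for a partly missing start date:

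1. Derive the earliest possible onset from the known month and year and, where available, the actual date of the visit after which the event appeared.
2. Count the event in a post-dose window (D0-D30, and D0-D7 where used) unless that earliest possible onset falls after the window. In that case assign it to the later interval.
3. Keep the present worst-case rule for events with no date information.
4. State that the rule applies to the SAE and MAAE windows.

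Align 5.3.1.5 with this. That section also contains a wider trigger: "If either the start or stop date is missing or partially missing, the time of onset will be considered to be missing". This conflicts with 4.2.1.2.4, where onset depends on the start and vaccination dates only. If programmed, it would move fully dated late events with an open stop date into D0-D30. The two sections must be reconciled.

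Cost: one SAP paragraph and a few lines of derivation code before database lock. Slightly fewer events are counted as early, but none that could have been early is removed.

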4.2.1.3 SAEs (including AESIs)

An event will be considered as a serious event if "Yes" is checked for "Serious" in the CRF.

An event will be considered as an AESI if "Yes" is checked for "Is the event an AESI?" in the CRF.

SAEs (including AESIs) will be analyzed throughout the study using the following periods:

- Within 7 days after vaccination
- Within 30 days after vaccination
- During the study (i.e., all SAEs occurred during the study), including the 6-month follow-up period

4.2.1.4 Medically-Attended Adverse Event (MAAE)

An event will be considered as an MAAE if "Yes" is checked for "Is the event an MAAE?" in the CRF.

MAAE will be analyzed during the following time periods:

- Within 7 days after vaccination
- Within 30 days after vaccination
- During the study (i.e., all MAAEs occurred during the study), including the 6-month follow-up period.

4.2.1.5 Other Safety Endpoints

4.2.1.5.1 Action Taken

This information will be summarized as collected, including missing observations. No derivation or imputation will be done.

4.2.1.5.2 Seriousness

This information will be summarized as collected. No derivation or imputation will be done.

4.2.1.5.3 **Outcome**

This information will be summarized as collected. No derivation or imputation will be done.

4.2.1.5.4 Causality

This information will be summarized as collected in the field "Relationship to Investigational Product". Missing causal relationship will be handled as described in Section 5.3.1.2. Relationship to study procedure is only presented in the listing.

4.2.1.5.5 AEs Leading to Study Discontinuation

This information will be summarized as collected. A flag is available in the clinical database for all AEs in order to identify AEs leading to discontinuation.

In general, the items that are counted are:

- Disposition table: A subject who on the "Completion at End of Study" form
- question "What was the participant's status?" has "Adverse Event" checked.
- Safety overview table: A subject who either on the "Completion at End of Study" form, question" What was the participant's status?" has "Adverse Event" checked or lists a solicited AE that has "Caused Study Termination" checked that is at least Grade 1 or an unsolicited AE that has "Caused Study Discontinuation" checked that is at least Grade 1 or missing and is within the time period indicated.
- System Organ Class/Preferred Term (SOC/PT) table: A solicited AE that has "Caused Study Termination" checked that is at least Grade 1 or an unsolicited AE that has "Caused Study Discontinuation" checked that is at least Grade 1 or missing and is within the time period indicated.

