4.1.1.2 Safety Endpoints

The endpoints for the evaluation of safety are:

- Occurrence, nature (Medical Dictionary for Regulatory Activities [MedDRA] preferred term), duration, intensity, and relationship to vaccination, and whether the event led to early termination from the study, of any unsolicited systemic AEs reported in the 30 minutes after each vaccination.
- Occurrence, time of onset, number of days of occurrence, intensity, action taken, and whether the reaction led to early termination from the study, of solicited (prelisted in

the subject's diary card and CRB) injection site reactions occurring up to D07 after each vaccination.

- Occurrence, time of onset, number of days of occurrence, intensity, action taken, and
 whether the reaction led to early termination from the study, of solicited (prelisted in
 the subject's diary card and CRB) systemic reactions occurring up to D07 after each
 vaccination.
- Occurrence, nature (MedDRA preferred term), time of onset, duration, intensity, action taken, relationship to vaccination, and whether the event led to early termination from the study, of unsolicited AEs up to D30 after each vaccination.
- Occurrence, nature (MedDRA preferred term), time of onset, duration, seriousness criteria, relationship to vaccination, outcome, and whether the event led to early termination from the study, of SAEs (including AESIs) throughout the trial from Visit 1 to the 6-month follow-up contact after the last vaccination.
- Occurrence, nature (MedDRA preferred term), time of onset, duration, intensity, action taken, relationship to vaccination, and whether the event led to early termination from the study for MAAEs throughout the trial, from Visit 1 to the 6-month follow-up contact after the last vaccination.

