4.2.1.1.3 Presence

Presence is derived from the maximum overall intensity on the period considered:

- None: No presence
- Grade 1, Grade 2, or Grade 3: Presence
- Unknown: Missing presence

Subjects with at least one non-missing presence for a specific endpoint will be included in the safety analysis. Conversely, those without a non-missing presence will not be included in the safety analysis of the endpoint.

The time period is displayed as D0-D3, D4-D7, D8 and later.

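### A solicited reaction flagged as ending participation but with no derivable intensity is left out of the SOC/PT discontinuation table, while an unsolicited AE in the same state is counted

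*SAP*

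**What the plan says.** SAP 4.2.1.5.5 opens with a general statement: "This information will be summarized as collected. A flag is available in the clinical database for all AEs". It then defines three counts.

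- **Disposition table:** uses only the end-of-study status Adverse Event.
- **Safety overview table:** counts an infant who "has 'Adverse Event' checked or lists a solicited AE" meeting the solicited condition, or who has an unsolicited AE meeting the unsolicited condition.
- **SOC/PT table:** uses the two event conditions alone, with no route through the end-of-study form.

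The solicited condition, up to the point where the unsolicited one begins, reads "solicited AE that has 'Caused Study Termination' checked that is at least Grade 1 or an unsolicited AE". The unsolicited condition is "an unsolicited AE that has 'Caused Study Discontinuation' checked that is at least Grade 1 or missing and is within the time period indicated". Both the overview and the SOC/PT bullets carry this difference.

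Missing intensity is a recognised state for solicited reactions. SAP 4.2.1.1.1 lists it among the daily intensity classes. It turns wholly missing daily records into None only when the CRF presence field is No, and not for fever even then. SAP 4.2.1.1.3 adds "Unknown: Missing presence" and removes such a subject from the analysis of that reaction. SAP 5.3.1.4 only refers back to 4.2.1.1.1.

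**The concern.** One count is built on two intensity rules, and the stricter rule falls on solicited reactions. The site has a box for recording that a reaction ended participation. Where that box is ticked but no intensity can be derived, the tick has no effect in the SOC/PT table, although the section's opening sentence promises no filtering.

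The item is a named part of the solicited-reaction endpoints in SAP 4.1.1.2: "whether the reaction led to early termination from the study, of solicited (prelisted in" the diary card and CRB. SAP Table 5.2 also asks for study discontinuation under solicited reactions, and for MedDRA terms under AEs leading to discontinuation. Of the three tables in 4.2.1.5.5, the SOC/PT table is the one that names the event. If the event drops out there, the study report can show an AE discontinuation that no preferred term explains.

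**Working it through.** The plan gives no figure to reproduce here, so the check applies the rules of SAP 4.2.1.5.5 to every type of record. Each event below is flagged as causing discontinuation and, if unsolicited, falls within the stated period.

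| Event and derived intensity | End-of-study status | Disposition | Overview | SOC/PT |
|---|---|---|---|---|
| Solicited, Grade 1 to 3 | Adverse Event | yes | yes | yes |
| Solicited, Grade 1 to 3 | other | no | yes | yes |
| Solicited, missing | Adverse Event | yes | yes | **no** |
| Solicited, missing | other | no | **no** | **no** |
| Unsolicited, Grade 1 to 3 | Adverse Event | yes | yes | yes |
| Unsolicited, Grade 1 to 3 | other | no | yes | yes |
| Unsolicited, missing | Adverse Event | yes | yes | yes |
| Unsolicited, missing | other | no | yes | yes |
| Either type, Grade 0 or None | Adverse Event | yes | yes | no |
| Either type, Grade 0 or None | other | no | no | no |

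The two event types part company only when intensity is missing.

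**Can a flagged solicited reaction be missing?** Yes. If the CRF records the reaction as present but holds no usable daily value, step 1 of SAP 4.2.1.1.1 does not apply because presence is not No. Step 2 has nothing to convert, and no later rule supplies a grade. Fever is the clearest example, because its grade depends on a temperature. SAP 5.3.1.3 sends partially missing temperatures to 4.2.1.1.1, which contains no rule for them. Protocol 5.1.3 has diary cards collected at the next visit, which a withdrawn infant may not attend.

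**How narrow is the case?**
- Maximum intensity is taken over the days (SAP 4.2.1.1.2), so one graded day suffices.
- A reaction too large to measure is Grade 3 (SAP 4.2.1.1.1).
- Site staff record solicited reactions seen in the 30-minute observation (protocol 9.1.1.3.1).
- Incomplete diary entries are followed up with the parents, and information missing from the diary can reach the CRB through the source document (protocol 11.1 and 13.2).

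The gap therefore needs every day to remain ungraded after these steps.

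**Which row of the table is likely?** Protocol 5.2.8 tells the investigator to record Adverse Event when a voluntary withdrawal is for safety concerns. Protocol 5.2.10 ranks that reason first and has the most significant reason checked. With correct completion, the third row applies: counted in disposition and overview, absent from SOC/PT.

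**The case against.** The best defence is that the asymmetry follows the SAP's own definitions. A solicited reaction is present only if its derived intensity is Grade 1 or higher (4.2.1.1.3). An unsolicited event needs only a verbatim term and an intensity other than Grade 0 (4.2.1.2.1). Section 4.2.1.5.5 applies each type's presence rule, so that no reaction is counted as ending participation while being left out of its own reactogenicity table. SAP 4.2.1.1.1 also accepts that a measurement may override the investigator's view that a reaction occurred.

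This explains the rule, and the consistency it buys is real. It does not justify the omission. The override makes sense where a measurement exists; here none does, and the site's record stands uncontradicted. Elsewhere the SAP keeps incomplete events in: a missing relationship counts as related (5.3.1.2), and a missing onset is included in the 30-day tables (4.2.1.2.4).

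A reader might also infer that withdrawals caused by reactions vanish from the report. The documents do not support that: the end-of-study status keeps the infant in two of the three tables when the form is completed as the protocol directs. Nor do they support the inference that families who withdraw over a reaction are the likeliest to leave the diary blank. That is plausible, but neither document says it.

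**Conclusion.** The point stands as a minor one. A flagged solicited reaction with no derivable intensity is excluded from the SOC/PT table, while an unsolicited AE in the same state is included. The main visible effect is an overview count with no matching preferred term. Only if the end-of-study form carries another status does the overview lose the infant as well.

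The size cannot be stated. The documents give no rate of AE discontinuation, no solicited share of it, and no frequency of ungraded reactions. A reader might be tempted to multiply guesses for the 2310 MenACYW infants: 2310 × 0.001 × 0.3 × 0.1 = 0.07 infants at the low end, and 2310 × 0.005 × 0.5 × 0.5 = 2.9 at the high end. Every factor after 2310 is an assumption and the results differ about forty-fold, so neither should be quoted as the effect.

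The direction is certain: the rule can only lower the count. It is identical in both groups and no hypothesis is tested, so the documents give no ground for claiming a between-group bias.

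**What to change.** In both the overview and SOC/PT bullets of SAP 4.2.1.5.5, add the words *or missing* to the solicited condition, so that it matches the unsolicited one. Show these events with intensity Missing, and state that this count is an exception to the presence rule in 4.2.1.1.3.

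Before database lock, reconcile every subject whose end-of-study status is Adverse Event against the SOC/PT table. This also brings out flagged events that derive to Grade 0 or None. Both conditions exclude those, and the change of wording leaves them excluded.

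The cost is two words in two bullets, one sentence on the exception, a small change to the table program and a reconciliation check. No new data are needed. The discontinuation count may become slightly less favourable, and a reaction may appear here that is absent from its own reactogenicity table; the stated exception explains why. If the sponsor prefers to keep the present rule, the minimum is a listing of flagged solicited reactions with missing intensity, together with the same reconciliation.
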